## **7.2.4 Sponsor Responsibility for Reporting Adverse Events**

All Adverse Events will be reported to regulatory authorities, IRB/IECs and investigators in accordance with all applicable global laws and regulations.

## **7.3 TRIAL GOVERNANCE AND OVERSIGHT**

### **7.3.1 Data Monitoring Committee**

To supplement the routine trial monitoring outlined in this protocol, an external Data Monitoring Committee (DMC) will monitor the interim data from this trial. The voting members of the committee are external to the Sponsor. The members of the DMC must not be involved with the trial in any other way (e.g., they cannot be trial investigators) and must have no competing interests that could affect their roles with respect to the trial. The DMC will include 2 clinicians experienced in urology/dermatology and 1 external statistician; this is in addition to the unblinded trial statistician who will be a non-voting member of the committee.

The DMC will make recommendations to the Sponsor regarding steps to ensure both subject safety and the continued ethical integrity of the trial. The DMC will review interim trial results, consider the overall risk and benefit to trial participants (see Section 8.1.5 - Interim Analyses) and recommend to the Sponsor if the trial should continue in accordance with the protocol.

Specific details regarding responsibilities and governance, including the roles and responsibilities of the various members and the Sponsor protocol team; meeting facilitation; the trial governance structure; and requirements for and proper documentation of DMC reports, minutes, and recommendations will be described in a separate charter that is reviewed and approved by the DMC. The DMC will monitor the trial at an appropriate frequency, as described in the detailed DMC charter. The DMC will also make recommendations to the Sponsor protocol team regarding steps to ensure both subject safety and the continued ethical integrity of the trial.

A DMC recommendation will be communicated to the Sponsor as agreed to in the Collaboration agreement based on reviewing the interim analysis results.

### **7.3.2 Clinical Adjudication Committee**

The HPV Vaccine Program Pathology Panel will be responsible for providing the definitive pathologic diagnoses of external genital lesion biopsies for study purpose (not for medical management). Slides from external genital lesion biopsies will be evaluated by HPV Vaccine Program Pathology Panel. The HPV Vaccine Pathology Panel will prepare reports on each tissue specimen without knowing the vaccination groups of subjects. A separate guideline that details the HPV Vaccine Program Pathology Panel process has been approved by the HPV Program Pathology Panel.

## 8.0 STATISTICAL ANALYSIS PLAN

### 8.1 Statistical Analysis Plan Summary

This section contains a brief summary of the statistical analyses for this trial. Full detail is in the Statistical Analysis Plan (SAP) (Section 8.2).

#### 8.1.1 Efficacy Analyses

The efficacy endpoints, analysis population, and statistical methods to be employed for the efficacy analyses are presented in Table 3. The Per-Protocol Efficacy population will consist of subjects who receive the full vaccination series within 1 year, and have 1 or more follow-up visits following Month 7, do not have any general protocol violations, and are seronegative at baseline and PCR-negative from baseline through Month 7 for the relevant HPV type.

Table 3 Summary of Analysis Strategy for Efficacy Endpoint

Endpoint/Variable (Description)	Statistical Method	Analysis Population	Missing Data Approach
Primary Objective			
HPV6/11/16/18 related persistent infection	Exact 95% CI for vaccine efficacy	PPE	Not imputed
PPE=Per-Protocol Efficacy. HPV=human papillomavins. CI=Confidence Interval			

The study is case-driven and the final analysis will be conducted at the time of 18 persistent infection cases collected, if no early stop for efficacy in interim analysis which is planned to be conducted at the time of 11 cases collected.

#### 8.1.2 Safety Analyses

All subjects who received at least 1 study vaccination and have follow-up data will be included in the analysis of safety. The primary interest for safety will be the incidence of vaccine-related serious adverse experiences, which will be summarized and tabulated.

#### 8.1.3 Immunogenicity Analyses

Anti-HPV6, 11, 16, 18 seroconversion percentages and Geometric Mean Titer (GMT) by Month 7 will be evaluated by computing point estimates and constructing 95% Confidence Intervals (CI) for all subjects, and for HM and MSM subjects, respectively.

#### 8.1.4 Power and Sample Size

This study will enroll approximately 1100 subjects. For Asian males in Protocol V501-020, the observed incidence rate for HPV6/11/16/18-related Persistent Infection among placebo recipients was 2.3 per 100 person-years with the vaccine efficacy of 100%. If the true incidence rate on HPV6/11/16/18-related Persistent Infection is 2.3 per 100 person-years in Japanese males, with the assumption of vaccine efficacy of 85%, about 59% of enrolled subjects with evaluable data and one interim analysis at time of 11 persistent infection cases collected, the study will have at least 90% power to achieve success for the primary hypothesis. With the assumption of vaccine efficacy of 90%, the study will have more than 98% power to achieve success for the primary hypothesis. The total number of persistent

infection cases needed to keep the power is 18. The statistical criterion for success requires that the lower bound of the two-sided 95% confidence interval for vaccine efficacy be greater than 0. The rate of drop-out is estimated as 0.41 based on Protocol V501-020. The details are as follows: no general protocol violation: 95%; exclusion rate due to Day1 seropositive or PCR positive between Day 1 and Month 7 to HPV 6, 11, 16, and 18 is not greater than 15%; 90% of randomized subjects completed vaccination phase and 80% of Month 7 subjects complete 30-month follow-up period.

### **8.1.5 Interim Analysis**

There is one planned interim analysis in this trial. The interim analysis will occur after 11 persistent infection cases are collected. The trial has >56% power to detect significant vaccine efficacy at  $\alpha=0.006$  one-sided in interim analysis if the true vaccine efficacy is 85%. A p-value of 0.6% for vaccine efficacy approximately corresponds to equal or less than 1 of 11 persistent infection cases occurring in the vaccine group.

## **8.2 Statistical Analysis Plan**

There are no plans to issue a separate Statistical Analysis Plan (SAP) for this trial. If, after the trial has begun, important changes are made that affect principal features of the primary or key secondary analyses, then the protocol will be amended, as appropriate (consistent with ICH Guideline E-9). Any other changes made to the planned analyses after the protocol has been finalized, along with an explanation as to when and why they occurred, will be listed in the Clinical Study Report (CSR) for the trial. Post hoc exploratory analyses will be clearly identified in the CSR.

### **8.2.1 Responsibility for Analyses**

The statistical analysis of the data obtained from this trial will be the responsibility of the Clinical Biostatistics department of the SPONSOR.

This study will be conducted as a double-blind study under in-house blinding procedures. The official, final database will not be unblinded until medical/scientific review has been performed, protocol violators have been identified, and data have been declared final and complete.

### **8.2.2 Trial Objectives**

See Section 3.0 for primary objectives.

### **8.2.3 Analysis Endpoints**

#### **8.2.3.1 Efficacy Endpoints**

(1) Primary Endpoint: the incidence of HPV 6-, 11-, 16- or 18-related persistent infection.

Persistent infection is defined to have occurred if any of the following occurs:

- The subject is positive by an HPV PCR assay (type 6, 11, 16, or 18) to at least 1 common gene for the given vaccine HPV type in 2 consecutive anogenital or biopsy samples collected at least 4 months apart; OR
  - The subject has Pathology Panel consensus diagnosis of condyloma acuminata, PIN, penile, perianal or perineal cancer AND detection of HPV 6, 11, 16 or 18 by Thinsection PCR in an adjacent section of the same biopsy block AND is PCR positive for the same HPV type to at least 1 common gene in the sample obtained at a separate adjacent visit, prior to or following the biopsy showing HPV disease.
- (2) Secondary Endpoint: combined incidence of HPV 6-, 11-, 16- or 18-related persistent infection, condyloma acuminata, PIN, penile, perianal or perineal cancer.

Disease is defined to have occurred if on a single biopsy or excised tissue, there is

- Pathology Panel consensus diagnosis of condyloma acuminata, penile/perianal/perineal intraepithelial neoplasia (PIN), penile, perianal or perineal cancer; AND
  - At least one of HPV types 6, 11, 16, or 18 is detected by Thinsection PCR in an adjacent section from the same tissue block.
- (3) Exploratory Endpoint: combined incidence of HPV 6-, 11-, 16- or 18-related condyloma acuminata

### **8.2.3.2 Immunogenicity Endpoints**

The immunogenicity endpoints are seroconversion percentages by Month 7 to each of HPV 6, 11, 16, and 18. Seroconversion is defined as changing serostatus from seronegative to seropositive. A subject with a cLIA titer at or above the serostatus cutoff for a given HPV type is considered seropositive for that type. The immunogenicity endpoint includes cLIA GMTs at each time point. On total IgG, same exploratory analysis will be conduct.

### **8.2.3.3 Safety Endpoints**

Safety assessment will focus on the injection site adverse experiences/vaccine-related adverse experiences prompted for on the VRC occurring Day 1 through Day 5 following any vaccination, elevated temperature from Day 1 to 5 following any vaccination and systemic adverse experiences/vaccine-related adverse experiences occurring Day 1 through Day 15 following any vaccination. Serious adverse experiences occurring Day 1 through Day 15 following any vaccination, serious vaccine-related adverse experiences and new medical condition occurring any time during the study will be summarized.

## **8.2.4 Analysis Populations**

### **8.2.4.1 Efficacy Analysis Population**

Three subject populations will be considered for the efficacy analyses: 1 per-protocol population and 2 modified intention-to-treat (MITT) populations. The efficacy analysis using the per-protocol population will be the primary analysis for the primary and the secondary endpoints related to HPV types 6, 11, 16 and 18. Supplemental analyses for those endpoints will be provided using the 2 MITT populations. The per-protocol and MITT populations differ with regard to the inclusion/exclusion of protocol violators who are described below.

The populations will be restricted to subjects who received at least 1 vaccination and have any follow-up visit. General protocol violators will be included. All efficacy cases occurring after Day 1 will be counted. The MITT population (also labeled as HNRT [Naïve to the Relevant HPV type]) will include only subjects who are seronegative and PCR-negative at Day 1 to the appropriate HPV types. In the MITT population, subjects who receive incorrect clinical material or an incorrect dose of vaccine will be included in the analysis in the group to which they were randomized.

**8.2.4.2 Immunogenicity Analysis Populations**

The primary analysis population will be the Per-Protocol Immunogenicity (PPI) population. To be included in this population, subjects must satisfy all the criteria for the PPE population, and additionally must:

- (1) have received all vaccinations within acceptable day ranges (see [Table 4](#))
- (2) have provided blood samples for serology testing within the acceptable day range (see [Table 5](#))

A supportive analysis of immunogenicity will be conducted on the All Naïve Subjects With Serology (ANSS) population. To be included in this population, subjects must have received at least one dose of study vaccine, must have provided serology data, and must have been seronegative at Day 1 and PCR-negative from Day 1 through Month 7 to the appropriate HPV types. Subjects who receive incorrect clinical material or an incorrect dose of vaccine will be included in the analysis in the group to which they were randomized. Immune responses at 4 weeks postdose 3 will also be summarized in subjects who are (1) seropositive and PCR negative at Day 1; (2) seronegative and PCR positive at Day 1; and (3) seropositive and PCR positive at Day 1, for the given HPV type.

Table 4 Acceptable Day Ranges for Vaccination Visits

Dose of 4-Valent HPV L1 VLP Vaccine Scheduled for Injection	Protocol Specified Visit Window	Day Range for Inclusion in Statistical Analysis (Relative to Day 1†)
Dose 1	Day 1†	0
Dose 2	Month 2 ± 3 weeks	36 to 84
Dose 3	Month 6 ± 4 weeks	148 to 218

† Day 1 refers to the date when dose 1 of 4-valent HPV L1 VLP vaccine is injected.

Table 5 Acceptable Day Ranges for Collection of Serum Samples

Study Visit	Sample Type	Target Collection Day (Relative to Day 1)†	Day Range for Inclusion in Statistical Analysis (Relative to Day 1)†
Day 1	Serum	0	-14 to 0
Month 7	Serum	30 days post dose 3	21 to 49 post dose 3
Month 36	Serum	1095	913 to 1277

† Day 1 refers to the date when dose 1 of 4-valent HPV L1 VLP vaccine is injected. For Month 7, indicated target collection/day range is relative to date of injection of dose 3 of 4-valent HPV L1 VLP vaccine.

### 8.2.4.3 Safety Analysis Population

All subjects who received at least 1 study vaccination and have follow-up data will be included in the analysis of safety.

### 8.2.5 Statistical Methods

#### 8.2.5.1 Statistical Methods for Efficacy Analyses

There are two efficacy analyses planned in this study. At the time when 11 cases of persistent HPV 6-, 11-, 16- or 18-related infection have been observed in the PPE population, an interim analysis will be conducted. If non-significant results are reached in the interim analysis, the final analysis will occur at the time of 18 cases of persistent HPV 6-, 11-, 16- or 18-related infection observed. The study conclusions regarding the vaccine efficacy will be made based on these analyses.

The primary efficacy hypothesis for vaccine efficacy >0% against persistent infection will be tested based on the number of cases among vaccine recipients relative to the total number of cases. A one-sided exact test based on a binomial distribution which conditions on the total number of cases will be used. The vaccine efficacy is defined  $(1 - R_{V501} / R_{\text{placebo}}) * 100$  [%], where  $R_{V501}$  and  $R_{\text{placebo}}$  are persistent infection incidence for V501 and placebo. The 95% confidence interval for the vaccine efficacy is calculated based on a proportion ( $p$ ) of V501 recipients among all cases. The exact 95% confidence interval for  $p$  is calculated based on F distribution, and the exact 95% confidence interval for vaccine efficacy can be computed from the confidence bounds for  $p$ . The estimate of vaccine efficacy is adjusted by the “ratio of the amount of follow-up” ( $k$ ), where  $k = (\text{total amount of follow-up in the placebo group} / \text{total amount of follow-up in the V501 group})$ . The relationship between  $p$  and the vaccine efficacy is as follows.

The point estimate of the vaccine efficacy ( $\hat{\pi}$ ) =  $[1 - p(1 + k)] / (1 - p)$

The 95% lower confidence limit for the vaccine efficacy =  $[1 - p_u(1 + k)] / (1 - p_u)$

The 95% upper confidence limit for the vaccine efficacy =  $[1 - p_l(1 + k)] / (1 - p_l)$

Where  $p_u$  and  $p_l$  are the upper and lower bounds of the exact confidence interval for  $p$  respectively.

Secondary efficacy endpoint and exploratory endpoint will be analyzed via the same manner used for the primary efficacy analysis.

Table 6 summarizes the efficacy analyses to be performed, and they are described in detail in the following sections.

Table 6 Efficacy Endpoints, Statistical Methods and Analysis Populations

Endpoint	Statistical Method	Analysis Population
Primary Endpoint: HPV6/11/16/18 related persistent infection		
Tests of Efficacy Hypotheses HPV 6/11/16/18 related persistent infection	Analysis of VE †	PPE
Supplementary Efficacy Analyses Overall and by HPV Type	Analysis of VE	PPE, HNRT, FAS
Impact of Baseline Characteristics Age, Sexual Orientation, Circumcision, Smoking, Lifetime Sexual Partners, Presence of Other HPV Types	Analysis of VE	PPE
Robustness of Persistent Infection Definition Persistent infection relaxing the 6 month (+/- 1 month) interval requirement (i.e., ≥ 0 months duration)	Analysis of VE	PPE
Persistent infection requiring 2, 3, or 4 consecutive positive results over ≥ 12 months duration	Analysis of VE	PPE
Robustness of DNA Detection Definition Incident DNA Detection at 1 or More Visits	Analysis of VE	PPE
Secondary Endpoint: HPV6/11/16/18 related persistent infection, condyloma acuminata, PIN, and penile/ perianal/ perineal cancer		
Tests of Efficacy Hypotheses HPV 6/11/16/18 related persistent infection and disease	Analysis of VE	PPE
Supplementary Efficacy Analyses Overall, by HPV Type, by Persistent Infection or Disease, by Lesion type	Analysis of VE	PPE, HNRT, FAS
Impact of Baseline Characteristics Age, Sexual Orientation, Circumcision, Smoking, Lifetime Sexual Partners, Presence of Other HPV Types	Analysis of VE	PPE
Other Endpoint		
Intra-anal persistent infection HPV 6/11/16/18-Related Intra-anal Persistent Infection – Overall, by HPV Type HPV 6/11/16/18-Related Intra-anal Persistent Infection – Overall, by Baseline Characteristics (Age, Sexual Orientation, Circumcision, Smoking, Lifetime Sexual Partners, Presence of Other HPV Types)	Analysis of VE Analysis of VE	PPE, HNRT, FAS PPE
Persistent infection excluding intra-anal persistent infection HPV 6/11/16/18-Related Persistent Infection excluding Intra-anal Persistent Infection – Overall, by HPV Type	Analysis of VE	PPE, HNRT, FAS
HPV 6/11/16/18-Related Persistent Infection excluding Intra-anal Persistent Infection – Overall, by Baseline Characteristics (Age, Sexual Orientation, Circumcision, Smoking, Lifetime Sexual Partners, Presence of Other HPV Types)	Analysis of VE	PPE
Time to Event Analysis Time to Occurrence of HPV 6/11/16/18-Related persistent infection	Kaplan-Meier Estimate	PPE, HNRT, FAS
Time to Occurrence of HPV 6/11/16/18-Related persistent infection and diseases	Kaplan-Meier Estimate	PPE, HNRT, FAS
Time to Occurrence of HPV 6/11/16/18-Related intra-anal persistent infection	Kaplan-Meier Estimate	PPE, HNRT, FAS
Time to Occurrence of HPV 6/11/16/18-Related persistent infection excluding intra-anal persistent infection	Kaplan-Meier Estimate	PPE, HNRT, FAS
Therapeutic Efficacy HPV 6/11/16/18-Related Persistent Infection – Overall, by HPV Type	Analysis of VE	Day 1 PCR- and Sero+
HPV 6/11/16/18-Related Intra-anal Persistent Infection – Overall, by HPV Type	Analysis of VE	Day 1 PCR- and Sero+
HPV 6/11/16/18-Related Persistent Infection excluding intra-anal persistent infection – Overall, by HPV Type	Analysis of VE	Day 1 PCR- and Sero+
Incidence of clearance of HPV 6/11/16/18 Infection	Estimation of Incidence ‡	Day 1 PCR+ and Sero-, Day 1 PCR+ and Sero+
† refers to point and confidence interval estimation of vaccine efficacy (1-relative risk) ‡ refers to point and confidence interval estimation of incidence, expressed as rate per 100 person-years HPV = Human Papillomavirus; VE = Vaccine Efficacy; PIN = Penile/Perianal/perineal intraepithelial neoplasia; PPE = Per-protocol efficacy; FAS = Full analysis set; HNRT = Naïve to the Relevant HPV type; PCR = Polymerase chain reaction; PCR+ = PCR positive; PCR- = PCR negative; Sero+ = Seropositive; Sero- = Seronegative		

#### Computation of Follow-Up Time

Follow-up for the primary analysis begins following the Month 7 visit. Therefore the follow-up time for a subject will be the interval in days between his Month 7 visit and his last day of follow-up. For cases, this will be the visit at which the biopsy detecting the endpoint was taken. If a subject develops more than one case of disease that fits into a given endpoint classification, the final visit date will be the date at which the first of these endpoints was detected. For non-cases, the last day of follow-up will be defined as the cutoff date when the database is locked for analysis. Follow-up time will be similarly calculated for secondary and exploratory endpoints.

For the MITT analyses, follow-up begins following Day 1 instead of Month 7, so the follow-up time for a subject will be the interval in days between the Day 1 visit and the last day of follow-up, as described above.

The date of occurrence of each endpoint is defined as follows. For disease cases, it is the date of the sample from which the diagnosis of disease was made. For persistent infection it is the date of the first consecutive sample which was positive for HPV by PCR.

Kaplan-Meier estimates of the time-to-event curves will be generated for certain efficacy endpoints. Subjects without the endpoint will be censored at the end of their follow-up time, as defined in this section.

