## 6.0 TRIAL FLOW CHART

Visit Number:	1	2	3	4	5	6	7	8	9
Scheduled Day/Month.:	Day 1	Month 2	Month 6	Month 7	Month 12	Month 18	Month 24	Month 30	Month 36
Visit Window  :		2 months after Day 1, ±3 weeks	6 months after Day 1, ±4 weeks	3 to 7 weeks after Month 6	12, 18, 24, 30 or 36 months after Day 1, ±4 weeks				
Administrative Procedures									
Informed Consent	X								
Informed Consent for Future Biomedical Research	X								
Inclusion/Exclusion Criteria	X								
Subject Identification Card	X								
Medical History	X								
Update Medical History (New condition not already recorded as medical history or adverse experiences)		X	X	X	X	X	X	X	X
Sexual History	X	X	X	X	X	X	X	X	X
Concomitant Medication Review 	X	X	X	X	X	X	X	X	X
Vaccine Allocation/Randomization	X								
V501 /Placebo Administration	X	X	X						
Clinical Procedures/Assessments									
Anogenital Physical Examination	X								
Vital Signs (height, weight, oral temperature, sitting pulse, blood pressure and respiration) 	X	X	X						
Provide Vaccination Report Card (VRC)	X	X	X						
Review and Collect VRC data		X	X	X					
Adverse Events Monitoring	X	X	X	X	X	X	X	X	X
Laboratory Procedures/Assessments									
Genitourinary examination for external genital lesions	X			X	X	X	X	X	X
Penile/glans penis file and wetted swab for HPV PCR 	X			X	X	X	X	X	X
Scrotal file and wetted swab for HPV PCR 	X			X	X	X	X	X	X
Perianal examination for external genital lesions	X			X	X	X	X	X	X
Perineal/perianal file and wetted swab for HPV	X			X	X	X	X	X	X

Visit Number:	1	2	3	4	5	6	7	8	9
Scheduled Day/Month:	Day 1	Month 2	Month 6	Month 7	Month 12	Month 18	Month 24	Month 30	Month 36
Visit Window  :		2 months after Day 1, ±3 weeks	6 months after Day 1, ±4 weeks	3 to 7 weeks after Month 6	12, 18, 24, 30 or 36 months after Day 1, ±4 weeks				
PCR 									
Intra-anal wetted swab for HPV PCR 	X			X	X	X	X	X	X
External genital lesion biopsy (if indicated) 		X	X	X	X	X	X	X	X
Serum for Anti-HPV 	X			X					X
STI Testing (local laboratory testing, if clinically indicated) 	X	X	X	X	X	X	X	X	X
Blood (DNA) for Future Biomedical Research 	X								

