### **7.1.4 Other Procedures**

#### **7.1.4.1 Withdrawal/Discontinuation**

When a subject discontinues/withdraws prior to trial completion, all applicable activities scheduled for the next scheduled visit should be performed at the time of discontinuation. Any adverse events which are present at the time of discontinuation/withdrawal should be followed in accordance with the safety requirements outlined in Section 7.2 - Assessing and Recording Adverse Events. If a subject must discontinue/withdraw after the Month 7 study visit, the subject should be asked to return for a final visit if it has been at least 4 months since the last trial visit. This visit would consist of the same specimen collections and tests conducted at the next scheduled visit and the subject would be formally discontinued from the study at the end of this visit. The discontinuation visit should not be done if it is medically contraindicated or if the subject refuses. If no discontinuation visit is performed, the subject should be formally discontinued from the study on the day the decision to discontinue is made. All attempts must be made to contact a subject who is lost to follow-up (a certified letter must be sent at the final attempt). Subjects who are lost to follow-up should be formally discontinued from the study on the day of the last unsuccessful attempt at contact.

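### Non-cases accrue follow-up to database lock rather than to their last HPV specimen, which overstates person-time and understates arm-level incidence and Kaplan-Meier risk; vaccine efficacy is little affected

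*Combined protocol and SAP*

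**What the plan says.** Section 8.2.5.1, Computation of Follow-Up Time, starts the primary-analysis clock at Month 7 (Day 1 for the MITT analyses). It then states: "For non-cases, the last day of follow-up will be defined as the cutoff date when the database is locked for analysis". For the curves: "Subjects without the endpoint will be censored at the end of their follow-up time, as defined in this section". The same method is extended to the secondary and exploratory endpoints. The event date is set separately: "For persistent infection it is the date of the first consecutive sample which was positive for HPV by PCR".

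The other relevant provisions are:

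- Section 8.2.3.1 builds the swab route to a case on type-specific PCR positivity "in 2 consecutive anogenital or biopsy samples collected at least 4 months apart"; the other route needs a biopsy plus a positive sample at an adjacent visit.
- After Month 7, the flow chart schedules specimens at "12, 18, 24, 30 or 36 months after Day 1, ±4 weeks".
- Section 7.1.4.1 gives some men who discontinue a final visit: "This visit would consist of the same specimen collections and tests conducted at the next scheduled visit". It also gives lost men an end date: "Subjects who are lost to follow-up should be formally discontinued from the study on the day of the last unsuccessful attempt at contact".
- Section 8.2.4.1 admits a man to the PPE population with a single visit after Month 7. Section 8.2.7 expects 80% of Month 7 subjects to complete follow-up.
- Section 8.2.5.1 defines efficacy from the incidences in the two arms and adjusts it by k, placebo follow-up divided by V501 follow-up. Table 6 lists Kaplan-Meier estimates in PPE, HNRT and FAS.
- Section 8.2 says: "There are no plans to issue a separate Statistical Analysis Plan (SAP) for this trial". This wording is therefore the operative rule.

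**The concern.** Follow-up should count the time in which an event could have been observed. A man last swabbed at Month 12 cannot become a case afterwards, but the rule keeps him in the denominator, and in the Kaplan-Meier risk set, until lock. The same applies to the gap between any man's latest specimen and the lock, and to completers' time after Month 36. Neither the discontinuation date nor the final specimen visit in Section 7.1.4.1 is used. Section 8.2.10 rules out imputing missing results, yet the rule in effect treats unsampled time as negative.

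What is at stake is descriptive. Incidence per arm would depend on when the database happens to be locked, and Kaplan-Meier risk would be too low. Section 4.2.1 intends a comparison with V501-020, so a denominator driven by the lock date is unhelpful. There is a secondary issue: if loss differs between arms, k calculated this way hides most of the difference it is meant to correct.

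**Working it through.** **The plan's own figures.** Table 8 can be reproduced without any person-time. With k = 1, the V501 share of cases is p = (1 − VE)/(2 − VE). Success is at most 1 of 11 at the interim or at most 4 of 18 at the final analysis. VE 85% gives 57.0% interim, 83.2% final given no early stop and 92.8% overall (stated: 57.0%, 83.1%, 92.7%). VE 90% gives 73.6%, 92.9% and 98.1% (stated: 73.6%, 93.0%, 98.1%). The power figures are untouched by this point.

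**Inputs.** From the documents: 20% loss after Month 7, and 2.3 per 100 person-years (Section 8.2.7); visits at 5, 11, 17, 23 and 29 months after Month 7 (flow chart); about 50 months' duration with 36 per subject (Section 1.0), implying about 14 months of entry. Assumed: 2.3 is the true hazard, loss has a constant hazard, every man is retained to Month 12, infections persist, and two consecutive positives are required.

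**1. Everyone locked at exactly 29 months after Month 7.** Loss hazard h = −ln(0.8)/29 = 0.007695 per month; S(t) = exp(−h(t − 5)); infection hazard 0.023/12 per month.

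- Mean time to dropout is 26.91 months (29/26.91 = 1.077). Mean time to last scheduled visit is 26.41 (29/26.41 = 1.098). If every eligible dropout attends the Section 7.1.4.1 visit, the mean is 26.69 (1.087).
- First positives at 5, 11, 17 and 23 months have probabilities 0.00954, 0.01133, 0.01120 and 0.01107. Multiplied by S at the confirming visit (0.9549, 0.9118, 0.8707, 0.8314), they sum to 0.0384 cases per man.
- Rate = 1200 × 0.0384 / person-months per man:

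| Non-case follow-up ends at | Person-months per man | Rate per 100 PY | Kaplan-Meier risk |
|---|---|---|---|
| Lock (plan) | 28.42 | 1.62 | 3.8% |
| Last specimen | 25.86 | 1.78 | 4.1% |
| Penultimate specimen | 20.14 | 2.29 | 4.3% |

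With all Section 7.1.4.1 visits attended, simulation gives 1.65 against 1.79, and 3.9% against 4.2%. Last-specimen censoring recovers (1.78 − 1.62)/(2.29 − 1.62), about a quarter of the shortfall. The rest arises because a first positive at a man's final specimen can never be confirmed.

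**2. Lock before completion, uniform 14-month entry (simulation).** Mean follow-up under the rule over last-specimen follow-up: month 36, 22.0/17.66 = 1.246; month 38, 24.0/19.90 = 1.206; month 44, 30.0/24.28 = 1.236. With no dropout at all, the excess is still 13% to 18%, because a man's latest specimen precedes the lock by some months. Rates are 1.23 to 1.41 under the rule and 1.53 to 1.74 at last specimen.

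**3. Lock at month 50.** 36/26.91 = 1.338 and 36/26.41 = 1.363. Completers' time after Month 36 alone gives 36/29 = 1.241; that part does not affect Kaplan-Meier risk up to Month 36.

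**4. Wider assumptions.** A simulation with 400 men per arm at Month 7, entry over 14 or 20 months and a lock lag of 0 or 3 months covered the 11-case, 18-case and end-of-study analyses. Placebo person-time was inflated by 25% to 61%. Kaplan-Meier risk at Month 30 was about 5% to 12% lower in relative terms. With equal loss, VE changed by less than 0.1 percentage point.

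**5. Unequal loss, 25% V501 and 15% placebo (illustrative).** Monthly hazards are −ln(0.75)/29 and −ln(0.85)/29. Under the rule, k reflects only retention to Month 12: exp(5 × (0.00992 − 0.00560)) = 1.022. Using time to dropout, k = 1.022 × 27.46/26.36 = 1.064. Using the last visit, k = 1.022 × 27.08/25.73 = 1.076. At 4 of 18 cases the exact upper limit pu is 0.4764, so the VE lower limit [1 − pu(1 + k)]/(1 − pu) is 7.0% under the rule, against 3.2% and 2.2%. The reverse split gives 11.0% against 14.5% and 15.4%.

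**The case against.** The strongest reply is that nothing inferential changes. The test conditions on case counts, and person-time enters VE only through k. The visible VE effect needs a loss imbalance that no section predicts and the least favourable passing split, and even then the lower limit stays above 0. That is correct, and no change in the primary decision is claimed.

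Table 6 lists efficacy estimates and Kaplan-Meier curves; its only output expressed per 100 person-years is clearance incidence. That also stands. However, Section 8.2.5.1 defines VE from arm incidences, and the Kaplan-Meier curves are listed outputs directly affected.

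The illustrations are loosely tied to the event schedule. Under the model in step 1, about 385 men per arm at Month 12 would yield 385 × 0.0384 × 1.15, about 17 cases by study end at VE 85%. The locks in step 2 therefore do not depict an 18-case analysis. The excess at that analysis was 33% to 54% in the wider simulation, against 21% to 25% in step 2, so the magnitude is unstable. The direction is not.

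The V501-020 follow-up convention is not given. The gap from 2.3 to 1.62 is thus a model result, not a measured error, and the effect on comparability is unknown.

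Finally, a specimen-based end date could censor a man who was examined for lesions but had no evaluable swab. This is marginal, because examinations and swabs fall at the same scheduled visits.

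**Conclusion.** The concern holds. As written, the rule counts unsampled time as event-free, and no other section overrides it. Person-time is overstated by roughly 8% to 10% in the most favourable setting examined and by 21% to 36% with staggered entry and no lock lag. Under longer enrolment and a lock lag it reaches about 60%. Kaplan-Meier risk is affected less: 3.8% against 4.1% in the simplest case. All of these rest on assumed accrual, loss pattern and lock timing.

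With similar loss by arm, k, VE and the primary test are essentially unchanged. With unequal loss, the rule mutes the k adjustment in either direction. This should be fixed, but it does not threaten the primary conclusion.

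**What to change.** - End non-case follow-up at the last visit with an evaluable HPV specimen (swab or biopsy, including a Section 7.1.4.1 discontinuation visit) on or before the data cutoff, and define evaluable.
- End case follow-up at the occurrence dates the section already gives: first positive sample for persistent infection, biopsy sample date for disease. The present follow-up sentence for cases mentions only a biopsy.
- Use these dates for person-time, k and Kaplan-Meier censoring in PPE, HNRT and FAS.
- State in the report that a non-case's final sampling interval cannot yield a confirmed persistent infection, and add a sensitivity analysis ending non-case follow-up for that endpoint at the penultimate specimen.

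The cost is amendment wording, one derivation from dates already collected and one extra analysis. Alpha, the 11 and 18 case counts and power do not change. The reported person-time will be smaller, and the main change removes only part of the understatement; the sensitivity analysis shows the rest.
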